5. TREATMENT PLAN

5.1 Treatment Regimen

The treatment to be used in this trial is outlined below in Table 2:

Table 2 Trial Treatment

Drug*	Dose/Potency	Dose Frequency	Route of Administration	Regimen/Treatment Period	Use
Pegylated Liposomal Doxorubicin	40 mg/m ²	Once every 4 weeks	IV infusion over one hour per FDA package insert	One cycle = 28 days	FDA approved treatment for platinum resistant ovarian cancer
Pembrolizumab	200 mg as a flat dose	Once every 3 weeks	IV infusion per the FDA package insert	One cycle = 28 days	Experimental

*The drugs may be held independent of one another, however, the study clock will not stop as far as determining the cycle/day of treatment.

If there are 2 DLTs within the first 6 patients during the safety lead-in, the dose of PLD will be lowered to 30 mg/m².

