5.2 Pre-Treatment Criteria

5.2.1 Cycle 1, Day 1

Participants must continue to meet all eligibility criteria prior to dosing on Cycle 1, Day 1, as outlined in Protocol Section 3.1.

5.2.2 Subsequent Cycles, on PLD treatment days: Patients must have all of the following:

Absolute Neutrophil Count: $\geq 1,500/\text{mcL}$
Hemoglobin: $\geq 9\text{g/dL}$
Platelets: $\geq 100,000/\text{mcL}$
Serum Creatinine $\leq 1.5 \times \text{ULN}$
Liver Function Test $\leq 2.5 \times \text{ULN}$
ECOG performance status of 0-1

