5.4 Definition of Dose-Limiting Toxicity (DLT)

Toxicities that are considered DLT toxicities that occur during the first 4 weeks of treatment will be monitored; if 2 out of the first 6 patients develop a DLT, the dose of PLD will be reduced to 30 mg/m².

Definition of DLT: Dose limiting toxicity (DLT) refers to both non-hematologic and hematologic toxicities deemed by the treating physician to be related to study treatment experienced during the first cycle (i.e. first 4 weeks) of treatment.

A DLT will be defined as any of the following, occurring during Cycle 1:

1. Non-Hematologic Toxicity

Any Grade 3 or 4 event, excluding:

- Fatigue
- Grade 3 nausea and/or vomiting controlled with supportive measures within 24 hours,
- Grade 3 constipation controlled with supportive measures within 24 hours,
- Grade 3 diarrhea controlled with supportive measures within 24 hours,
- Grade 3 hypophosphatemia,
- Grade 3 hyponatremia,
- Grade 3 hypomagnesemia
- Grade 3 rash that does not resolve to grade 2 or grade 1 within \leq 5 days

2. Hematologic Toxicity

- Grade 4 neutropenia of > 7 day's duration
- Febrile neutropenia (a disorder characterized by an ANC $< 1000/\text{mm}^3$ and a single temperature of $> 38.3^\circ\text{C}$ (101°F) or a sustained temperature of $\geq 38^\circ\text{C}$ (100.4°F) for more than one hour.
- Dose delay of greater than 3 weeks (21 days) due to failure to recover counts.
- Grade 4 thrombocytopenia or bleeding associated with grade 3 thrombocytopenia.
Any other hematologic toxicities of Grade 4
Requirement for repeated blood transfusion within 4-6 weeks

3. Any study treatment related death.

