6.1 Dose modifications for Pegylated Liposomal Doxorubicin

If patients experience treatment-related toxicities, their PLD dose should be reduced according to institutional prescribing and dose-reduction standards per the below tables.

If greater than two dose reductions are required, discussion and approval must be obtained by the Overall PI.

Recommended dose reductions for PLD (Doxil) per the FDA package insert:

Hand Foot Syndrome	
Toxicity	Dose Adjustment
Hand Foot Syndrome	
Grade 1: Mild erythema, swelling, or desquamation not interfering with daily activities	
• If no previous Grade 3 or 4 HFS, no dose adjustment.• If previous Grade 3 or 4 HFS, delay dose up to 2 weeks, then decrease dose by 25%.
Grade 2: Erythema, swelling, or desquamation interfering with, but not precluding normal physical activities; small blisters or ulcerations less than 2 cm. in diameter.	
• Delay dosing up to 2 weeks or until resolved to grade 0 or 1.• Discontinue doxil if no resolution after 2 weeks.• If resolved to grade 0 or 1 within 2 weeks: and no previous grade 3 or 4 HFS, continue treatment at previous dose or And previous Grade 3 or 4 toxicity; decrease dose by 25%
Grade 3: Blistering, ulceration, or swelling interfering	
• Delay dosing up to 2 weeks or until resolved to grade 0 or 1,

with walking or normal daily activities; cannot wear regular clothing.	
 then decrease dose by 25% • Discontinue doxil if no resolution after 2 weeks
Grade 4: Diffuse or local process causing infectious complications, or a bed ridden state or hospitalization.	
 • Delay dosing up to 2 weeks or until resolved to grade 0 or 1, then decrease dose by 25% • Discontinue doxil if no resolution after 2 weeks

Stomatitis

Toxicity	Dose Adjustment
Stomatitis	
Grade 1: Painless ulcers, erythema, or mild soreness	
 • If no previous Grade 3 or 4 toxicity, no dose adjustment. • If previous Grade 3 or 4 toxicity, delay dose up to 2 weeks, then decrease dose by 25%.

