10. STUDY CALENDAR

Baseline evaluations are to be conducted within 14 days prior to start of protocol therapy. Baseline labs must be performed within 14 days of treatment initiation. Scans and x-rays must be done ≤ 4 weeks prior to the start of therapy. In the event that the participant's condition is deteriorating, laboratory evaluations should be repeated within 48 hours prior to initiation of the next cycle of therapy.

Assessments must be performed prior to administration of any study agent. Study assessments and agents should be administered within ± 3 days of the protocol-specified date, unless otherwise noted.

	Pre-Study	C1 D1	C1 D8	C1 D15	C1 D22	C2 D1	C2 D15	C3 D1	C3 D8	Cycle 4 and beyond^f	Off Study ^c
PLD ^d		A				A		A		A	
Pembrolizumab ^e		B			B		B		B	B	
Informed consent	X										
Demographics	X										
Medical history	X										
Concurrent meds	X	X-								X ^f	
Physical exam ¹	X	X			X	X	X	X	X	X ^f	X
Vital signs ²	X	X			X	X	X	X	X	X ^f	X
Height and weight ³	X	X			X	X	X	X	X	X ^f	
Performance status ⁴	X	X			X	X	X	X	X	X ^f	X
CA-125	X	X				X		X			X
CBC w/diff, plts	X	X	X	X	X	X	X	X	X	X ^f	X
Serum chemistry ^a	X	X	X	X	X	X	X	X	X	X ^f	X
TSH	X	X				X					X
EKG (as indicated)	X										
Adverse event evaluation		X-								X ^f	X
Tumor measurements	X	Tumor measurements are repeated every 8 weeks ± 1 week weeks. Documentation (radiologic) must be provided for participants removed from study for progressive disease. ^g									X
B-HCG	X ^b										
FFPE blocks ^d	X										
ECHO or MUGA ^e	X									X ^e	

A: PLD 40 mg/m² IV every 28 days ± 3 days window

B: Pembrolizumab 200 mg IV every 21 days ± 3 days window

1: Will include skin examination in addition to physical exam

2: Including blood pressure, temperature, respiratory rate, heart rate

3: Height should be performed at screening and Cycle 1 Day 1 only, weight should be performed at each visit

4: ECOG performance status as per Appendix 1.

5: The schedules for pembrolizumab and doxil can be delayed independently, however, the clock does not stop for each 28 day cycle regarding the cycle/day.

- a: Albumin, alkaline phosphatase, total bilirubin, bicarbonate, BUN, calcium, chloride, creatinine, glucose, LDH, phosphorus, potassium, total protein, SGOT [AST], SGPT [ALT], sodium.
- b: Serum pregnancy test (only for women of childbearing potential).

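### The DLT item for count-related dose delay is first met on day 51, after the Cycle 1 window closes, and the lead-in dose decision may be taken before it is known

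*Combined protocol and SAP*

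**What the plan says.** Section 5.4 opens its list with the condition "A DLT will be defined as any of the following, occurring during Cycle 1", and glosses the first cycle as the first 4 weeks. Section 13.1 uses the same 4-week window for the primary safety endpoint. One of the hematologic items is "Dose delay of greater than 3 weeks (21 days) due to failure to recover counts".

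PLD is given every 28 days and pembrolizumab every 21 days (section 5.1 and the section 10 calendar). Either drug may be held, but section 5.1 says "the study clock will not stop as far as determining the cycle/day of treatment", and a calendar footnote repeats that "the clock does not stop for each 28 day cycle regarding the cycle/day". The count thresholds for re-treatment in section 5.2.2 apply to PLD days: "Subsequent Cycles, on PLD treatment days: Patients must have all of the following".

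Section 13 lowers PLD from 40 to 30 mg/m² if 2 of the first 6 patients have a DLT. With no more than 1, the dose is taken as the MTD and 20 more patients are enrolled. Section 13.3 asks that the six complete at least one cycle and that safety data be reviewed before further enrolment.

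**The concern.** A delay of more than three weeks in a drug given every four weeks cannot be complete within the first four weeks. The definition therefore contains an item that its own window excludes, and no sentence assigns a late cycle 2 dose back to Cycle 1. Two investigators could classify the same patient differently.

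The patients at stake have prolonged cytopenia that meets none of the other items. Examples are Grade 2-3 neutropenia without fever, Grade 2-3 thrombocytopenia without bleeding, or hemoglobin below the 9 g/dL needed on PLD days without Grade 4 anemia or repeat transfusion. For them the delay item is the only stated route into the 2-of-6 count.

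Section 6.1 does not fill the gap. For hand-foot syndrome and stomatitis it sets a limit, "Discontinue doxil if no resolution after 2 weeks". The neutropenia and thrombocytopenia table gives no maximum delay. These events would still appear in the toxicity summary and could reach the DSMC, but neither of those sets the PLD dose for the next 20 patients.

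**Working it through.** **Inputs.** DLT window: days 1-28 (5.4, 13.1). PLD dose 2: day 1 + 28 = day 29. Pembrolizumab dose 2: day 1 + 21 = day 22. Visit window: ±3 days (section 10). Decision rule: continue at 40 mg/m² if at most 1 of 6 has a DLT (section 13).

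**1. The plan's own table.** The probability of continuing is (1-p)^6 + 6p(1-p)^5.

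| True DLT rate | 0.1 | 0.2 | 0.3 | 0.4 | 0.5 | 0.6 | 0.7 |
|---|---|---|---|---|---|---|---|
| Section 13.1 | 89% | 66% | 42% | 23% | 11% | 4% | 1% |
| Recomputed | 88.6% | 65.5% | 42.0% | 23.3% | 10.9% | 4.1% | 1.1% |

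All seven agree after rounding (at 0.2 the unrounded value is 65.54%). The table is right for whatever DLT rate applies.

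**2. When the item is first met.** A dose is first more than 21 days late on its due day + 22.
- PLD: 29 + 22 = day 51 (48 to 54 if the due day moves by ±3).
- Pembrolizumab: 22 + 22 = day 44 (41 to 47).

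Every one of these days is after day 28. For PLD the gap is 51 - 28 = 23 days.

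**3. Who is unobserved at the earliest permitted review.** When the sixth patient reaches day 28, a patient who started k days earlier is on day 28 + k. Reaching day 51 needs 28 + k ≥ 51, so k ≥ 23. Patients with k below 23, always including the sixth (k = 0), have not reached the point where the item can be judged. Section 13.2 gives no accrual rate, so the number of such patients is unknown.

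**4. Effect on the decision, given one delay-only patient.** If exactly one of the six has only this event and it is not counted, the decision changes when exactly one of the other five has a countable DLT. With patients independent, the probability is 5p(1-p)^4:
- p = 0.1: 5 × 0.1 × 0.9^4 = 0.328
- p = 0.2: 5 × 0.2 × 0.8^4 = 0.410
- p = 0.3: 5 × 0.3 × 0.7^4 = 0.360

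**5. Unconditional illustration.** The documents give no rate for delay-only patients, so the rates here are assumed. Take a 20% rate for all other DLTs and add 1%, 5% or 10% of patients who meet only the delay item. Counting the item would lower the chance of continuing at 40 mg/m² from 65.5% to 63.1%, 53.4% or 42.0%: about 2, 12 or 24 points. The loss is smaller if the item is attributed to Cycle 1 and some early patients have passed day 51 by the review.

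**The case against.** The strongest reply is that 5.4 speaks of toxicities experienced in the first cycle. The toxicity is the low count, and the length of the delay only measures its severity. On that reading, counts suppressed in Cycle 1 that hold up the next dose do qualify, and a reading that voids one of the protocol's own items should be doubted. This stands to the extent that a reader should not conclude the item is certainly dead. It does not settle the matter, because no text makes the attribution and section 13.3 does not make the review wait for it.

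It is also fair that one cycle is a minimum, that CBCs on days 8, 15, 22 and C2D1 would usually show a persisting cytopenia, and that the DSMC sees toxicity data. So the signal is not hidden. But permission to wait is not a requirement, and a visible low count is not a counted DLT.

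The remaining class is narrow. Febrile neutropenia, Grade 4 thrombocytopenia, bleeding with Grade 3 thrombocytopenia, other Grade 4 hematologic events and repeat transfusion are all DLTs in their own right.

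A reader might extend the argument to "Grade 4 neutropenia of > 7 day's duration" and infer that an episode starting late in Cycle 1 escapes too. Section 5.4 does not support that: it does not require the duration to be completed by day 28, and it can be established a few days later. The item "Requirement for repeated blood transfusion within 4-6 weeks" has no stated starting point, but this point does not depend on it.

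**Conclusion.** The concern holds as an internal conflict in the primary safety rule. On the literal text the delay item can never count. On the attributed reading, a team that follows section 13.3 exactly can fix the dose and reopen enrolment before a listed DLT can be known. The conflict does not depend on which drug is late or on the ±3-day window; day 51 itself assumes the nominal PLD schedule.

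Its size is uncertain. The 33% to 41% applies only once a delay-only patient exists, and rests on independence and on other-DLT rates taken from the 13.1 table. A reader might take it as the chance of a wrong dose decision in this trial. The documents give no rate that would support that. Nor is there an arithmetic error in section 13.1: the fault lies in the definition and the timing of the review.

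**What to change.** In 5.4 and 13.1, state that a delay of more than 21 days in the cycle 2 PLD dose, caused by counts suppressed in Cycle 1, counts as a Cycle 1 DLT.

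In 13.3, hold the lead-in review until the sixth patient's C2D1 CBC. If any lead-in patient's PLD is then being held for counts, wait until that patient recovers, has a DLT, stops PLD for another reason, or reaches day 51. PLD holds for hand-foot syndrome, stomatitis or scheduling would not trigger the wait.

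The cost is a few sentences. The C2D1 CBC is already scheduled. The extra wait is at most 51 - 29 = 22 days, about 3 weeks, and arises only when a lead-in patient's counts have not recovered. Eligibility admits hemoglobin of exactly 9 g/dL, which is also the re-treatment threshold, so a small fall in one patient could start the wait; it would end as soon as that patient recovers.

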5.5 General Concomitant Medication and Supportive Care Guidelines

5.5.1 Concomitant Medications/Vaccinations (allowed & prohibited)

Medications or vaccinations specifically prohibited in the exclusion criteria are not allowed during the ongoing trial. If there is a clinical indication for one of these or other medications or vaccinations specifically prohibited during the trial, discontinuation from trial therapy or vaccination may be required. The investigator should discuss any questions regarding this with the Overall Principal Investigator, who will then contact the Merck Clinical team as needed. The final decision on any supportive therapy or vaccination rests with the Overall Principal Investigator and/or the participant's primary physician.

5.5.2 Acceptable Concomitant Medications

All treatments that the investigator considers necessary for a participant's welfare may be administered at the discretion of the investigator in keeping with the community standards of medical care. All concomitant medication will be recorded on the case report form (CRF) including all prescription, over-the-counter (OTC), herbal supplements, and IV medications and fluids. If changes occur during the trial period, documentation of drug dosage, frequency, route, and date may also be included on the CRF.

All concomitant medications received within 28 days before the first dose of trial treatment and 30 days after the last dose of trial treatment should be recorded. Concomitant medications administered after 30 days after the last dose of trial treatment should be recorded for SAEs and ECIs (Events of Clinical Interest) as defined in Section 7.2.

5.5.3 Prohibited Concomitant Medications

Participants are prohibited from receiving the following therapies during the Screening and Treatment Phase (including retreatment for post-complete response relapse) of this trial:

- Antineoplastic systemic chemotherapy or biological therapy
- Immunotherapy not specified in this protocol
- Chemotherapy not specified in this protocol
- Investigational agents other than pembrolizumab
- Radiation therapy

Note: Radiation therapy to a symptomatic solitary lesion or to the brain may be allowed after discussion with the Overall PI..

- Live vaccines within 30 days prior to the first dose of trial treatment and while participating in the trial. Examples of live vaccines include, but are not limited to, the following: measles, mumps, rubella, varicella/zoster, yellow fever, rabies, BCG, and typhoid vaccine.

- Systemic glucocorticoids for any purpose other than to modulate symptoms from an event of clinical interest of suspected immunologic etiology. The use of physiologic doses of corticosteroids may be approved after consultation with the Overall PI and Sponsor.

Participants who, in the assessment by the investigator, require the use of any of the aforementioned treatments for clinical management should be removed from the trial.

The Exclusion Criteria describes other medications which are prohibited in this trial.

There are no prohibited therapies during the Post-Treatment Follow-up Phase.

5.6 Criteria for Taking a Participant Off Protocol Therapy

Duration of therapy will depend on individual response, evidence of disease progression and tolerance. In the absence of treatment delays due to adverse event(s), treatment may continue until one of the following criteria applies:

- Disease progression
- Intercurrent illness that prevents further administration of treatment
- Unacceptable adverse event(s)
- Participant decides to withdraw from the protocol therapy
- General or specific changes in the participant's condition render the participant unacceptable for further treatment in the judgment of the treating investigator
- Participant has completed 35 treatments (approximately 2 years) with pembrolizumab (Note: participant may continue on study receiving only PLD at the discretion of the treating investigator)

Participants will be removed from the protocol therapy when any of these criteria apply. The reason for removal from protocol therapy, and the date the participant was removed, must be documented in the case report form (CRF). Alternative care options will be discussed with the participant.

Regarding length of duration of treatment of PLD, investigator should follow the FDA package insert for PLD.

Before participants continue on PLD for more than 8 cycles, the treating physician must confer with the Overall PI and obtain approval to do so.

If participants are removed from PLD therapy because of PLD toxicities, they are tolerating Pembrolizumab, and there is no evidence of RECIST progression, participants may continue on Pembrolizumab alone after discussion and approval from the Overall PI.

For Centralized Subject Registrations, the research team submits a completed Off Treatment/Off Study form to ODQ when a participant comes off study. This form can be found on the ODQ website or obtained from the ODQ registration staff. Other investigative sites will inform the Project Manager as soon as a participant is taken off protocol therapy. The Project Manager will then make the relevant updates in OnCore.

For Decentralized Subject Registrations, the research team updates the relevant Off Treatment/Off Study information in OnCore.

In the event of unusual or life-threatening complications, treating investigators must immediately notify the Overall PI,

- [name]. at [contact].

5.7 Duration of Follow Up

Participants will be followed for 4 weeks after removal from protocol therapy for adverse events. Participants will be followed for survival. Follow-up will be reported in 3 month intervals for up to two years after removal from study treatment or until death, whichever occurs first. Participants removed from protocol therapy for unacceptable adverse event(s) will be followed until resolution or stabilization of the adverse event.

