Grade 2: Painful erythema, edema or ulcers but can eat.	
 • Delay dosing up to 2 weeks or until resolved to grade 0 or 1. • Discontinue doxil if no resolution after 2 weeks. • If resolved to grade 0 or 1 within 2 weeks: 
and no previous grade 3 or 4 HFS, continue treatment at previous dose
 
or
 
And previous Grade 3 or 4 toxicity; decrease dose by 25%

Grade 3: Painful erythema, edema or ulcers and cannot eat.	
 • Delay dosing up to 2 weeks or until resolved to grade 0 or 1. Decrease dose by 25% and return to original dose interval • Discontinue doxil if no resolution after 2 weeks
Grade 4: Diffuse or local process causing infectious complications, or a bed ridden state or	
 • Delay dosing up to 2 weeks or until resolved to grade 0 or 1, then decrease dose by 25% and

hospitalization.	
 return to original dose interval • Discontinue doxil if no resolution after 2 weeks
------------------	--

Neutropenia and Thrombocytopenia

Toxicity	Dose Adjustment
Neutropenia and Thrombocytopenia	
Grade 1	No dose reduction
Grade 2	Delay until ANC \geq 1500 and plts \geq 100,000; resume treatment at previous dose
Grade 3	Delay until ANC \geq 1500 and plts \geq 100,000; resume treatment at previous dose
Grade 4	Delay until ANC \geq 1500 and plts \geq 100,000; resume at 25% dose reduction or continue previous dose with prophylactic granulocyte growth factor.

6.2 Dose Modifications for Pembrolizumab:

Adverse events (both non-serious and serious) associated with pembrolizumab exposure may represent an immunologic etiology. These adverse events may occur shortly after the first dose or several months after the last dose of treatment. Pembrolizumab must be withheld for drug-related toxicities and severe or life-threatening AEs as per Table 3 below. See Section 6.3.1 and Events of Clinical Interest Guidance Document for supportive care guidelines (**Appendix B**), including use of corticosteroids.

Table 3

Dose Modification Guidelines for Drug-Related Adverse Events (Please also see Appendix B)

Toxicity	Hold Treatment For Grade	Timing for Restarting Treatment	Discontinue Participant

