7.1. Expected Toxicities

7.1.1 PLD

The most common adverse reactions observed with DOXIL are asthenia, fatigue, fever, nausea, stomatitis, vomiting, diarrhea, constipation, anorexia, hand-foot syndrome, rash and neutropenia, thrombocytopenia and anemia.

Other more rare toxicities include:

1) Cardiac toxicity: Special attention must be given to the risk of myocardial damage from cumulative doses of doxorubicin HCl. Acute left ventricular failure may occur with doxorubicin, particularly in patients who have received a total cumulative dosage of doxorubicin exceeding the currently recommended limit of 550 mg/m². Lower (400 mg/m²) doses appear to cause heart failure in patients who have received radiotherapy to the mediastinal area or concomitant therapy with other potentially cardiotoxic agents such as cyclophosphamide. Prior use of other anthracyclines or anthracenodiones should be included in calculations of total cumulative dosage. Congestive heart failure or cardiomyopathy may be encountered after discontinuation of anthracycline therapy. Patients with a history of cardiovascular disease should be administered

DOXIL only when the potential benefit of treatment outweighs the risk. Cardiac function should be carefully monitored in patients treated with DOXIL. The most definitive test for anthracycline myocardial injury is endomyocardial biopsy. Other methods, such as echocardiography or multigated radionuclide scans, have been used to monitor cardiac function during anthracycline therapy. Any of these methods should be employed to monitor potential cardiac toxicity in patients treated with DOXIL. If these test results indicate possible cardiac injury associated with DOXIL therapy, the benefit of continued therapy must be carefully weighed against the risk of myocardial injury.

2) Infusion reactions: Acute infusion-related reactions were reported in 7.1% of patients treated with DOXIL in the randomized ovarian cancer study. These reactions were characterized by one or more of the following symptoms: flushing, shortness of breath, facial swelling, headache, chills, chest pain, back pain, tightness in the chest and throat, fever, tachycardia, pruritus, rash, cyanosis, syncope, bronchospasm, asthma, apnea, and hypotension.

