7.3 Expedited Adverse Event Reporting

7.3.1 Investigators **must** report to the Overall PI any serious adverse event (SAE) that occurs after the initial dose of study treatment, during treatment, or within 30 days of the last dose of treatment on the local institutional SAE form.

7.3.2 For multi-institution studies where a DF/HCC investigator is serving as the Overall Principal Investigator, each participating institution **must** abide by the reporting requirements set by the DF/HCC. This applies to any medical event equivalent to an unexpected grade 2 or 3 with a possible, probable or definite attribution, both expected (unless listed in the protocol as not requiring expedited reporting) and unexpected grade 4 toxicities, and grade 5 (death) regardless of study phase or attribution.

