- c: Off-study evaluation. Patients will be followed for 4 weeks post treatment for adverse events. Patients will be followed for survival every 3 months for two years or until death, whichever occurs first.
- d: Obtained as part of eligibility criteria and will include PDL1 and nanostring analysis
- e: Up to a week before cycle 4 of PLD, and subsequent cycles (every 3 cycles).
- f: Physical exam, vital signs, PS as well as the following labs: CBC with plts, serum chemistry should be performed on a treatment day regardless if patients are receiving PLD alone, pembrolizumab alone or both agents.
- g: Immunotherapeutic agents such as pembrolizumab may produce antitumor effects by potentiating endogenous cancer-specific immune responses. The response patterns seen with such an approach may extend beyond the typical time course of responses seen with cytotoxic agents and can manifest a clinical response after an initial increase in tumor burden or even the appearance of new lesions. Patients with initial PD will be allowed to stay on trial with a repeat scan in 4 weeks. If repeat imaging confirms PD, patients will be discontinued from study therapy.

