- If IV steroids followed by high dose oral steroids does not reduce initial symptoms within 48 to 72 hours, treat with additional anti-inflammatory measures. Discontinue additional anti-inflammatory measures upon symptom relief and initiate a prolonged steroid taper over 45 to 60 days. If symptoms worsen during steroid reduction, initiate a retapering of steroids starting at a higher dose of 80 or 100 mg followed by a more prolonged taper and administer additional anti-inflammatory measures, as needed
- Add prophylactic antibiotics for opportunistic infections.

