3.12 Follow-up to Resolution

Subjects should be followed to resolution. The Adverse Experience eCRF should be updated with information regarding duration and clinical course of the event. Information obtained from the consulting specialist, including diagnosis, should be recorded in the appropriate AE fields. Free-text fields should be used to record narrative information:

- Clinical course of the event
- Course of treatment
- Evidence supporting recovery
- Follow-up to the clinical course

Any treatments administered for the event should also be entered in the Concomitant Medication eCRF.

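### Scheduled adverse-event collection stops 4 weeks after therapy (SAEs at 30 days), although the protocol names immune and cardiac toxicities that can start later

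*Combined protocol and SAP*

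**What the plan says.** **Collection windows.** Section 5.7: "Participants will be followed for 4 weeks after removal from protocol therapy for adverse events". Study calendar, note c: "Patients will be followed for 4 weeks post treatment for adverse events". Section 7.3.1 requires SAEs to reach the Overall PI if they occur after the initial dose and up to a limit: "within 30 days of the last dose of treatment on the local institutional SAE form". Survival follow-up then continues at 3-month intervals for up to two years (5.7 and note c). The one extension of adverse-event follow-up in 5.7 is for participants taken off therapy because of an unacceptable event, who are followed until it resolves or stabilizes.

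**Expected timing of toxicity.** Section 6.2, on pembrolizumab: "These adverse events may occur shortly after the first dose or several months after the last dose of treatment". Section 7.1.1, on PLD: "Congestive heart failure or cardiomyopathy may be encountered after discontinuation of anthracycline therapy".

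**Text that looks beyond day 30.** Section 5.5.2: "Concomitant medications administered after 30 days after the last dose of trial treatment should be recorded for SAEs and ECIs". It cites Section 7.2 for the definition of these events. Appendix B sections 1 and 2 require ECIs to be reported within 24 hours of awareness, whatever their attribution, and recorded in the study database. Appendix B 3.12 adds: "Subjects should be followed to resolution".

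**Use of the data.** Estimating the toxicity of the combination is secondary objective 1.3.1. Section 13.5 summarizes treatment-related toxicity by maximum grade and term, with 95% confidence intervals for secondary endpoints, and states no time cut-off.

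**The concern.** The plan names two kinds of toxicity that can arise after treatment has ended, then stops scheduled collection of new events at about one month. A month-two immune event or a later cardiac event is captured only if the site happens to learn of it and recognizes a duty to report. Missed events can only lower the reported toxicity, so any error makes the combination look safer. With 26 patients, a few events change the picture. The rules for what happens after day 30 also differ between sections, so two sites could follow the protocol in good faith and record different things.

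**Working it through.** The plan states no figure that depends on the adverse-event window, so there is none to reproduce. As background, the rule of 10 of 26 gives exact alpha 0.091 and power 0.916 for 25% versus 50%, and the DLT table in 13.1 reproduces. None of these moves with the window. The check is mainly a comparison of sections.

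1. **Windows against follow-up.** Four weeks is 28 days. The first 3-month follow-up falls at about day 91, so the window covers 28/91 = 31% of that interval. Against two years it covers 28/730 = 3.8% (30/730 = 4.1% for SAEs). These are shares of calendar time, not of risk.

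2. **Start of the clock.** Section 5.7 counts from removal from therapy, note c from the end of treatment, and 7.3.1 from the last dose. If removal is decided when the next 3-weekly pembrolizumab dose is due, the 5.7 window runs to day 21 + 28 = 49 after the last pembrolizumab dose. If no PLD was given in between, the SAE window has already closed at day 30.

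3. **Rules after day 30.** Section 5.5.2 assumes SAEs and ECIs will still be recorded, but Section 7.2 covers CTCAE grading, expedited-reporting exceptions and attribution. It neither defines ECIs nor gives a window. Section 7 sends ECIs to Appendix B for reporting. Appendix B section 2 sends the reader back to Section 7 on timelines, at least for overdose and drug-induced liver injury. Neither gives an end date for ECIs.

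4. **Ongoing events.** Appendix B 3.12 follows ECIs to resolution without condition. Section 5.7 does so only when the event caused removal. The gap is practical: for refractory Grade 3–4 pneumonitis, Appendix B 3.1 says "initiate a prolonged steroid taper over 45 to 60 days". A taper of that length started on the day of removal would end 45 − 28 = 17 to 60 − 28 = 32 days after the 5.7 window.

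5. **Cardiac events.** The Appendix B ECI list includes myocarditis and pericarditis at any grade, and any Grade 3 or higher event judged immune-related. Heart failure and cardiomyopathy are not listed. The calendar ties ECHO/MUGA to PLD cycles and shows none off study.

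6. **Illustration only.** The documents give no late-event rate. For an assumed rate p of late new-onset events, the expected count is 26p and the chance of at least one is 1 − (1 − p)^26:

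| Assumed p | Expected patients | Chance of at least one |
|---|---|---|
| 2% | 0.5 | 41% |
| 5% | 1.3 | 74% |
| 10% | 2.6 | 94% |
| 15% | 3.9 | 99% |

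For scale, 0 of 26 gives an exact 95% interval of 0 to 13.2%, and 3 of 26 gives 2.4% to 30.2%.

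**The case against.** The strongest reply is that serious late immune events do have a route into the data. Appendix B's ECI duty has no end date, applies regardless of attribution and covers any Grade 3 or higher event judged immune-related. Section 7.6 asks for all adverse events on the toxicity forms, and 13.5 sets no cut-off, so a late event that is reported can enter the table. This stands. A reader might infer that late events simply go uncounted; the documents do not support that.

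Nor do they support the inference that a participant who progresses with open Grade 3 colitis or pneumonitis is lost at day 28. Both are ECIs, 3.12 says they are followed to resolution, and nothing says 5.7 overrides it. What remains is a conflict between the two sections.

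The cardiac risk can also be overstated. Section 7.1.1 gives no interval after discontinuation. Prior anthracycline and low LVEF are excluded. Eight PLD cycles give 8 × 40 = 320 mg/m², below the 400 and 550 mg/m² levels in 7.1.1, and going further needs Overall PI approval. A participant who stops PLD but continues pembrolizumab remains under collection. These points reduce the expected number of events; they do not create a way to record one after both drugs stop.

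Finally, Section 5.7 says survival follow-up is reported every 3 months, not that the participant is seen, and Section 5.5.3 allows any therapy in that period. Late events may be thinly documented and hard to attribute. That is a fair limit on what the fix can deliver.

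**Conclusion.** The concern holds in a limited form. Scheduled collection of new adverse events ends before the late onset that 6.2 describes and may miss the post-treatment cardiac events in 7.1.1. Awareness-based ECI reporting partly fills the immune gap and does not list heart failure or cardiomyopathy. The sections on what is recorded after day 30 need to be reconciled.

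The consequence is a possible downward bias in the secondary toxicity estimate. Its size cannot be derived: Section 6.2 attaches no number to its time frame, no late-event rate is given, and how much the ECI duty would recover is unknown. It would be tempting to say that half or more of the risk period is unobserved, but that treats calendar time as risk and supplies an onset range the protocol does not give. The 2% to 15% range above is an assumption showing only that the count could run from under one patient to about four. The DLT endpoint (first 4 weeks of treatment) and the clinical-benefit endpoint are unaffected.

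**What to change.** - In 5.7, 7.3.1 and calendar note c, use one defined starting point and collect SAEs and ECIs through a stated longer window that reaches the first 3-monthly survival follow-up, for example 90 days after the last dose of either agent. The 90 days is a suggestion, not a figure from the documents.
- At later 3-monthly follow-up, record new related SAEs, naming heart failure and cardiomyopathy explicitly, and the start of any new anticancer therapy so that attribution can be judged.
- Reconcile 5.7 with Appendix B 3.12 so that the outcome of every ongoing ECI is recorded whatever the reason for stopping therapy.
- Correct the reference in 5.5.2 so that it points to the ECI definition in Appendix B, and give the ECI duty an end date.
- State in 13.5 the window used for the toxicity summary. Showing events within 30 days and later events separately would keep the confounded ones visible.

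The cost is protocol wording and a safety question at follow-up already planned, with no new visit or procedure. If that follow-up is now done from records alone, sites would need somewhat more effort to grade and attribute events. Some late events will be confounded by later therapy, and reported toxicity may be slightly higher.
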